#### 1.4 Utilizing SPECT to measure the dopamine transporter in PD patients

A key component of our program is to evaluate the effects of NAC on dopamine, using SPECT imaging, the relative function of key dopamine-containing regions of the brain in PD patients receiving oral and IV NAC. Specifically, we will plan to study changes in the dopamine transporter (DAT) which reflects the overall health of the dopaminergic system. DAT availability declines with age and declines more rapidly in patients with PD. By measuring the DAT binding before and after receiving approximately 90 days of nutritional support, we can evaluate whether either of the arms receiving supplements helps to support dopamine function.

The DAT mediates the reuptake of free dopamine from the synaptic cleft back into the axonal bouton (40). The DAT complex includes a dopamine receptor portion, which is exposed to the intrasynaptic milieu. When free dopamine in the intrasynaptic space binds to the receptor portion, a conformational change occurs in the structure of the transporter complex that physically moves, or “transports”, dopamine across the axonal membrane against a concentration gradient. Once inside the axonal bouton, structurally intact dopamine molecules can then be conserved by being repackaged within the storage vesicles. Alternatively, the level of dopamine, and hence the tone of the dopaminergic system, can be reduced by oxidative enzymes in the cytoplasm that make it unavailable for another transmission. The rate at which dopamine is removed from the synaptic cleft is one of the primary mechanisms for maintaining constant dopaminergic tone. As a result, the regional concentration of transporters tends to reflect the tone of the dopamine nervous system in that area (41,42). This has made the DAT the focus of research in many neuropsychiatric diseases in which dopamine dysfunction has been implicated.

Dopamine transporters may become one of the primary markers for Parkinson's disease in living patients for several reasons. They are living parts of the neurons that are most affected by the disease, and reflect their health. They are physically coupled with almost all of the diencephalic cells that become dysfunctional. This explains why messenger RNA levels for the dopamine transporter are decreased in the midbrains of patients with Parkinson's disease. Neuroimaging

studies reflect the same phenomenon by visualizing decreased transporter binding in the basal ganglia, that is, the distant regions to which the affected nigral cells project.

Studies of the presynaptic dopamine transporters in patients with symptomatic Parkinson's disease have been consistently positive, regardless of whether PET (43,44) or SPECT (45) imaging agents have been used. Exquisite sensitivity may reflect the observation that transporter concentrations decrease more rapidly than the number of axon terminals in animal models (46). This tends to keep the intrasynaptic levels of free dopamine constant. If the capacity of the sick neurons to produce dopamine decreases, then reducing the rate at which dopamine is removed from the synaptic cleft tends to move intrasynaptic dopaminergic levels back toward normal. This suggests that the transporter can be an effective marker for studying longitudinal changes in dopaminergic tone, and thus help to assess the effectiveness of interventions to treat PD.

One of the most widely used tracers for the evaluation of the DAT in PD patients is I-123 isoflupane (FP-CIT or DaTSCAN). This tracer is approved for clinical use in the US. A number of research studies have shown that DaTSCAN is able to differentiate PD from controls (47,48) and other related disorders (49,50). DaTSCAN has also been shown to correlate with disease severity (51,52). Finally, DaTSCAN and related tracers have been utilized for the evaluation of different therapeutic interventions (53,54). For these reasons, DaTSCAN is an excellent tracer for evaluating whether oral supplementation as described in this study, supports dopamine function in the brain of PD patients.

Thus, a key component of our program is to evaluate, using SPECT imaging, the relative function of key dopamine-containing regions of the brain in PD patients receiving oral and IV NAC. Specifically, we will plan to study changes in the dopamine transporter (DAT) which reflects the overall health of the dopaminergic system. DAT availability declines with age and declines more rapidly in patients with PD. By measuring the DAT binding before and after receiving approximately 90 days of nutritional support, we can evaluate whether receiving NAC helps to support dopamine function. The SPECT DaTScan is capable of determining the improvements in dopamine function associated with NAC.

## 1.6 Utilizing Magnetic Resonance Spectroscopy (MRS) to measure changes in the chemical milieu in brain of PD patients

It will also be beneficial to assess whether there are specific changes in levels of different molecules that are related to energy consumption and oxidative stress. Proton MR spectroscopy (1H-MRS) has been previously performed in Parkinson's disease (PD) and parkinsonian syndromes to evaluate in vivo concentrations of basal ganglia and cerebral cortex metabolites such as N-acetylaspartate (NAA), choline (Cho), and creatine (Cr) (55). This technique has been used to evaluate both the basal ganglia and motor cortex in PD patients (56,57). For example, one study showed a significant reduction in the NAA/Cr ratio in the motor cortex of PD patients compared with controls. Other studies have revealed inconclusive findings in the basal ganglia in PD patients. However, several studies have observed changes in MRS in PD patients in response to therapy. For example, one study demonstrated that after 6 months of therapy with pergolide, PD patients showed an improvement in motor performances and an increase in Cho/Cr ratios in

the motor cortex (58). The authors concluded that dopaminergic therapy capable of improving motor function might restore the Cho/Cr ratio in the motor cortex. While there are no MRS studies of glutathione concentrations in PD patients, the glutathione level is associated with the level of oxidative stress and has been measured in several other pathological conditions such as head trauma, stroke, and Alzheimer's disease (59,60,61). Thus, we plan to include MRS as an additional biomarker to evaluate the potential effects of the nutritional supplements and/or NAC on oxidative stress and cerebral activity in PD patients.

## **2.0 OBJECTIVES**

- 2.1 Evaluate Nutritional Supplementation with intravenous/oral NAC.
  - 2.1.1 To evaluate if oral supplementation or intravenous/oral NAC as described below helps to support dopamine function in the brain of patients with PD by measuring clinical symptoms.
  - 2.1.2 To evaluate whether intravenous/oral NAC helps to support dopamine function in the brain of patients with PD by measuring changes in the dopamine transporter using DaTScan SPECT imaging.
  - 2.1.3 To evaluate whether intravenous/oral NAC as described below helps to support changes in oxidative stress and metabolism, as measured by magnetic resonance spectroscopy (MRS), in patients with PD.

## **3.0 STUDY PLAN**

### **3.1 Subject Recruitment**

[figure not shown]
Subjects may be pre-screened by telephone using a standardized script and screening form. Verbal consent and HIPAA Authorization to obtain the prescreening information will be obtained from subjects prior to the prescreening interview. If subjects are prescreened in person, a signed consent and HIPAA Authorization to obtain prescreening information will be obtained. Information collected during pre-screening will be incorporated into the research records as source documentation for subjects included in the study. If subjects are not eligible to participate in the study they will be asked if the information provided in during prescreening maybe retained for consideration in other studies. Prescreening information will be retained for an indefinite period on an official screening form that will be kept in a secure locked area that will only be used by persons involved with research with this research Study.

We plan on recruiting up to 65 subjects over 3 years with the goal of recruiting 28 subjects who will receive approximately 90 days of combined intravenous/oral NAC, and then 14 subjects who will be in the waitlist control group receiving standard of care to be evaluated initially and then approximately 90 days later. This will allow for an attrition rate of up to one third. At the conclusion of the study, those in the waitlist control group will be given the option to receive a trial of oral/intravenous NAC if the data suggests that NAC is effective. All of the study subjects must be clinically diagnosed with PD by a referring neurologist. Subjects may be assessed using

structured examinations (i.e., the Unified Parkinson's Disease Rating Scale (UPDRS) or Movement Disorder Society (MDS) Unified Parkinson's Disease Rating Scale (MDS-UPDRS) and/or the Hoehn and Yahr scale. Diagnostic criteria will be applied using structured questionnaires, clinical interviews, and neurological examinations. Additional information is gathered, whenever possible, from family members, caregivers, review of previous medical records, and physical and laboratory examination. Subjects may take PD medications, but must be on a stable dose for at least 1 month prior to entering into the study.

To receive a diagnosis of clinically probable Parkinson's disease, the disease must be progressive, and at least two of the three cardinal signs of PD must be present (bradykinesia, rigidity, and tremor). Additionally, at least two of the following must also exist: (a) asymmetry of signs, (b) asymmetry at onset, (c) absence of characteristics of alternative diagnoses, (d) absence of another etiology known to cause similar features (e.g. neuroleptics).

### 3.1.1 Flow Chart

### **3.1.2 Inclusion criteria**

1. Clinical diagnosis of PD
2. Age 30-80 years old
3. Physically independent, ambulatory
4. Hoehn and Yahr score of I-III inclusive.
5. On stable antiparkinsonian medication for at least one month
6. Women of childbearing potential will confirm a negative pregnancy test and must practice effective contraception during the period of pilot study. In addition, male subjects who have a partner of childbearing age should practice effective contraception.

### **3.1.3 Exclusion criteria**

1. Known allergy to iodine, cobalt, or NAC that will be given in the study.
2. Previous brain surgery.
3. Score on Mini-Mental Status examination of 25 or lower.
4. Wheelchair-bound or bed-ridden, non-ambulatory.
5. Intracranial abnormalities that may complicate interpretation of the brain scans (e.g., stroke, tumor, vascular abnormality affecting the target area).
6. History of head trauma with loss of consciousness > 48 hours.
7. Any medical disorder or physical condition that could reasonably be expected to interfere with the assessment of parkinsonian syndrome symptoms, or with any of the study assessments including the SPECT imaging.
8. Patients with evidence of a significant psychiatric disorder by history/examination that would prevent completion of the study will not be allowed to participate.
9. Patients with current alcohol or drug abuse
10. Pregnant or lactating women.
11. Enrollment in active clinical trial/ experimental therapy within the prior 30 days.
12. Pending surgery during the course of the study.
13. History of very low blood pressure.
14. History of thrombocytopenia or clotting disorders.
15. Cancer patients receiving active chemotherapy.
16. History of active gallstone problems or a bile duct obstruction.
17. Severe gastroesophageal reflux disease.
18. History of uncontrolled diabetes, asthma, gastroesophageal reflux disease, thyroid conditions.
19. History of severe kidney disease (if a patient reports this problem, a serum creatinine will be checked to assess GFR and if it is less than 30, they will be excluded),
20. History of Leber's disease, a hereditary eye disease.
21. History of uncontrolled hypercalcemia
22. History of active sarcoidosis, histoplasmosis, or lymphoma.

23. Patients taking medications that might interact with NAC involved in this study will be evaluated on a case by case basis by the PI or study physician. These medications include: Medications for high blood pressure; Medications that slow blood clotting; Medications for diabetes; Nitroglycerin.

### 3.2 Registration Guidelines and Recruitment

Study subjects initially will be recruited by referral from the Jefferson Movement Disorders Clinic and local neurology groups. If any recruitment materials are developed, they will not be distributed without IRB approval.

The subject population is derived from the greater Philadelphia area, which represents a racially and economically diverse population. We will make efforts for this protocol to be widely accessible, including offering the procedures protocol without charge to the subject.

### 3.3 Treatment Plan:

3.3.1 Informed consent will be obtained from all subjects before protocol specific activities are carried out. The subject will be informed about the limited data on oral supplementation and intravenous/oral NAC to support brain health in PD patients, possible risks and benefits, and possible adverse events. Informed consent will be documented by use of written consent form approved by the Institutional Review Board at Thomas Jefferson University and signed by the subject or the subject's legal guardian. History, physical and neurological examination, and initial SPECT and MRS procedures (see below) will begin within 14 days of the informed consent process. Subjects will be receive either intravenous/oral NAC, or be placed on the waitlist control.

After approximately 90 days of receiving the supplements, subjects will undergo a follow up evaluation, which includes repeat neurological assessments, SPECT, and MRS. Note that subjects will continue taking the oral NAC until the scans are completed. Subjects will also continue to take their current Parkinson's medication regimen so that they will continue to receive standard of care treatment throughout the study. It is hoped that their standard of care treatment will remain constant throughout the course of the study, but their referring neurologist may adjust their medications as medically necessary.

3.3.2 N-Acetylcysteine will be obtained from the Jefferson Pharmacy (NAC is also called Acetadote; Cumberland Pharmaceuticals). NAC is an intravenous (IV) medication for the treatment of acetaminophen overdose. Acetylcysteine is the nonproprietary name for the N-acetyl derivative of the naturally occurring amino acid, L-cysteine (N-acetyl-L-cysteine, NAC). Acetadote is supplied as a sterile solution in vials containing 200 mg/mL acetylcysteine. The pH of the solution ranges from 6.0 to 7.5. Acetadote contains the following inactive ingredients: 0.5 mg/mL disodium edetate, sodium hydroxide (used for pH adjustment), and Sterile Water for Injection, USP.

For the oral supplement, NAC is obtained by the Jefferson Pharmacy at [name] and supplied by Vital Nutrients (produced under GMP) as a 600mg capsule of N-acetyl cysteine. The following inactive ingredients are also included: Ascorbyl Palmitate, Gelatin, Rice, Silica. The capsules contain no coatings, binders, fillers, or dairy, wheat, eggs, soy, yeast, commercial sugars, starch, preservatives, or hydrogenated oil.

NAC doses will be prepared for each patient by the study nurse. The dose will be 50mg/kg in approximately 200ml of D5W infused over approximately one hour 1x per week. The IV bag containing NAC is labeled as a research medication. Subjects will also receive 600mg NAC tablets supplied by the Jefferson Pharmacy and will take 1 tablet 2x per day on the days that they do not receive the IV NAC.

### 3.4 Criteria for Removal from / Cessation of Protocol

3.4.1 Measuring Endpoints: Endpoints will be measured after receiving oral/intravenous NAC, or being on the waitlist for 90 days. Any serious adverse events also will result in immediate discontinuation of the subject from the study.

3.4.2 Subject Withdrawal: The subject may withdraw from the study at any time for any reason.

3.4.3 Missing Appointments: Missing a total of 5 or more days of the supplements or 5 doses of the intravenous NAC as per the PI.

All reasons for discontinuation of procedure will be documented in study flow sheets.

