### 3.5 Adverse Events

The OHRP defines an adverse event as “any untoward or unfavorable medical occurrence in a human subject, including any abnormal sign, symptom, or disease, temporally associated with the subject’s participation in the research.” Adverse events can additionally be classified as an unanticipated problem, meaning it was not expected to occur during the course of the research. If an unexpected adverse event were to occur, it then needs to be determined whether or not it is due to the research being conducted. If the event is a result of the research procedures, most likely the event is directly connected to the subject’s participation in the research. It is also vital to determine whether an adverse event is serious. The OHRP defines a serious adverse event as one that a) results in death, b) is life-threatening, c) results in patient hospitalization or prolongation of existing hospitalization, d) results in persistent or significant disability/incapacity, e) results in congenital anomaly, or f) jeopardizes the subject’s health to the point where they may need medical or surgical intervention. If the adverse event is unexpected, related to the research, and serious (where it is causing harm to subjects), then it is also classified as an unanticipated problem and must be reported to the Thomas Jefferson University Hospital IRB. All adverse events will be reported in accordance with Jefferson IRB Adverse Events Report. The IRB shall be notified in a written safety report if any serious and unexpected adverse

experience associated with the use of the oral or intravenous nutritional supplements occurs.

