## 4.0 RISKS

**4.1 N-acetyl cysteine:** Oral NAC has few side-effects and is commonly used as an over-the-counter supplement worldwide. Oral NAC has good, but variable absorption from the gut (69,70), making it problematic as the sole mode of supplementation in a clinical study. Injectable NAC is used at lower doses for exercise fatigue and higher doses primarily as a liver protector. The dosages in this study are consistent with those used in the exercise physiology literature (71). Side effects increase with higher dosage, and the most common associated adverse reactions in the literature attributed to IV NAC administration are rash, urticaria, and pruritus. The frequency of adverse events has been reported to be between 0.2% and 20.8%, and they most commonly occur during the initial loading dose of acetylcysteine at dosages higher than what will be used in this study. Other side effects with greater than 1% occurrence include nausea and bronchospasm, again at higher dosages. A hypersensitivity reaction to NAC has been reported as a rare occurrence. NAC should be used with caution in patients with asthma. Please note that the oral and intravenous NAC dose used in this study is the same as one we have used in a study of NAC in women with breast cancer. We have found the NAC to be generally well tolerated at the doses we will be using in the current study.

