## 4.2 Oral NAC/intravenous Supplements:

### 4.2.1 Supplements, Doses, and Risks

General Risks: No formal interaction studies have been performed in the literature. Thus, it is possible that they may interact with each other and produce side effects as described below or additional side effects. Any supplement could result in an allergic reaction. We will ask subjects to report any unusual feelings they have while receiving the supplements. In addition, the supplements could interact with different medications. We will evaluate to determine if patients are taking any of the following:

1. Medications for high blood pressure.
2. Medications that slow blood clotting.
3. Medications for diabetes.
4. Nitroglycerin.

We will review each patient's medications to determine if there may be some potential risk for taking the NAC. For medications used for moderate to severe conditions as determined by the PI, subjects will be excluded. For medications used for mild conditions, we will discuss with the patient and also their doctor how to closely monitor any changes in their response to the medications while on the study.

**4.3 Potential Risks of DaTScan:** The I-123 DaTSCAN is a commercially available radioactive tracer that will be used according to its dose, route, and indication, but results in some exposure to ionizing radiation. The amount is acceptable for the research subjects who will directly benefit by receiving full clinical reads of these scans that their referring physician can utilize for determination of prognosis and treatment planning. Subjects will be required to lie still on the imaging table for 30-60 minutes, which can be uncomfortable.

**4.4 Special Risk Factors:** Injection of DaTscan requires the routine clinical pre-administration of Lugol's solution in order to protect the thyroid from radioactive exposure. The Lugol's solution is usually given in juice; it sometimes causes people to have a temporary strange taste in their mouth or a feeling of discomfort in their salivary glands.

**4.5 Risks of venous cannulation:** Venous cannulation is a routine clinical procedure that carries minimal risks when performed by trained personnel. It is possible that bruising could occur in some subjects. There is a theoretical risk of phlebitis or infection, which is very remote.

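### Section 3.4 does not separate stopping NAC from leaving the study, so the 90-day data of NAC subjects who tolerate it poorly may be lost selectively

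*Combined protocol and SAP*

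**What the plan says.** Section 3.4 gives three routes out of the protocol.

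- **Serious adverse event (3.4.1):** "Any serious adverse events also will result in immediate discontinuation of the subject from the study". This ends study participation, not only NAC, and applies in both arms.
- **Withdrawal by the subject (3.4.2):** at any time.
- **Missed dosing (3.4.3):** "Missing a total of 5 or more days of the supplements or 5 doses of the intravenous NAC as per the PI". The sentence does not say why the dose was missed.

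Section 3.3.2 sets the dosing: one infusion a week, with oral NAC on the days without an infusion. Section 3.3.1 places the follow-up clinical, SPECT and MRS evaluation at about 90 days. Section 4.1 says that "the most common associated adverse reactions in the literature attributed to IV NAC administration are rash, urticaria, and pruritus".

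Sections 3.8.4 and 3.8.5 randomize 2:1 to NAC or waitlist. The plan recruits up to 65 subjects for targets of 28 and 14 and allows for attrition of up to one third.

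**The concern.** In a randomized comparison, follow-up should not depend on how well a subject tolerates one of the treatments. Waitlist subjects take no NAC during the comparison, so they cannot miss a NAC dose, and 3.4.3 can remove people from only one arm. Doses withheld because of a suspected NAC reaction would be counted in the same way as doses forgotten. The serious-event rule is written for both arms, but it adds to the imbalance if NAC causes any such events.

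If these subjects leave before the second scan, the NAC arm at 90 days over-represents people who tolerated the drug. Section 3.8.4 describes the study mainly as a pilot to obtain an effect size for larger trials, so a selective loss would carry into their planning.

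**Working it through.** The plan states no figure on this point to reproduce. The check sets the dosing schedule against the 3.4.3 threshold, looks for text elsewhere that secures follow-up, and then sizes the consequence.

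**1. Dosing days (3.3.1, 3.3.2).** 90/7 = 12.9. Infusions on days 1, 8, ..., 85 make 13, or 12 if the last is not given. Oral days are 90 − 13 = 77 or 90 − 12 = 78. I read the supplement days in 3.4.3 as oral NAC days.

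**2. Effect of a safety hold.**
- A 7-day hold of both forms misses 6 oral days and 1 infusion. Since 6 ≥ 5, the criterion is met.
- A single hold of 4 oral days does not meet it (4 < 5).
- The rule counts a total, so two 3-day oral holds do (3 + 3 = 6).

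**3. The two limbs compared.** Oral: 5/78 = 6.4% to 5/77 = 6.5% of scheduled days. Infusion: 5/13 = 38% to 5/12 = 42% of scheduled doses. A short hold reaches the oral limb first.

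**4. Is the 90-day assessment secured elsewhere?**
- 3.3.1 and 3.7.1 say when the second evaluation happens. They do not say what happens to a subject who has stopped NAC.
- 3.6.1 asks for data on everyone registered, treated or not, but only as the protocol requires. It does not schedule a 90-day visit after removal.
- 3.8 defines no analysis population and no handling of missing 90-day data.

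**5. Recruitment margin (3.8.4).** 42/(1 − 1/3) = 63, close to the 65 planned. At 2:1, 65 × 2/3 ≈ 43 and 65/3 ≈ 22, giving margins of 43 − 28 = 15 and 22 − 14 = 8.

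**6. Numbers and power, as a ceiling.** Section 4.1 reports adverse event frequencies of 0.2% to 20.8% for IV NAC, most commonly at higher doses than here. Suppose every such subject were lost.
- Of 43 randomized to NAC, that is 0.1 to 8.9 subjects, inside the margin of 15.
- Of 28, it is 0.1 to 5.8.
- For power I use a two-sided t test at 0.05 with SD 10%. The noncentrality is δ/(SD × √(1/n₁ + 1/n₂)). At δ = 10%, 28 and 14 give 3.06 and power of 85%; 22 and 14 give 2.92 and power of 81%. At δ = 7.5%, power goes from 61% to 57%.

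**7. Why spare recruitment does not help.** Let f be the fraction of the NAC arm lost, and D the difference in mean change between retained and lost subjects. The retained mean differs from the full-arm mean by f × D. Sample size does not appear in that expression. The documents give no D. If D is assumed to be 5 or 10 percentage points (the plan's expected range of improvement), the shift at f = 20.8% is 1.0 or 2.1 points. At f = 0.2% it is 0.01 or 0.02 points. If D is zero there is no shift, and its sign is unknown.

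**The case against.** The other side has a good deal of substance.

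- **Automatic removal.** A reader might infer that a 7-day hold forces a subject out. The text does not say so: 3.4.3 sits under a heading about missed appointments and leaves the decision to the PI, who may keep the subject. This stands. The arithmetic shows when the criterion is met, not that removal follows.
- **Assessment conditional on finishing NAC.** A reader might infer this from 3.3.1 and 3.7.1. Read that way, they would also exclude waitlist controls, who are plainly assessed at 90 days. They describe timing. What remains is that no text secures the visit after NAC stops.
- **A safety hole.** Known NAC allergy and pregnancy appear only as entry exclusions ("Known allergy to iodine, cobalt, or NAC that will be given in the study"; "Pregnant or lactating women"), and 3.4 names no dosing action if either arises later. A reader might infer that subjects are left unprotected. The documents do not support that. Section 3.5(f) already counts as serious an event that jeopardizes health "to the point where they may need medical or surgical intervention". Section 4.2.1 says "We will ask subjects to report any unusual feelings they have while receiving the supplements", and for subjects taking listed medicines for mild conditions it plans discussion with them and their doctor of "how to closely monitor any changes in their response to the medications while on the study". Exclusion 23 provides case-by-case medication review, contraception is required, and a pregnancy test precedes SPECT. For milder reactions, ordinary clinical judgement would apply.
- **Little impact.** Section 4.1 describes these doses as generally well tolerated, the study is a pilot, and power hardly moves. This limits the size of the point. It does not answer selective loss.
- **Unseen material.** The flow chart is not shown. The point concerns the protocol text as available.

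**Conclusion.** The point holds in this form: Section 3.4 treats stopping NAC and leaving the study as one event. One of its removal criteria can act only in the NAC arm and does not exempt doses held for safety. Followed as written, with the PI choosing to remove, it can take poor tolerators out of one arm of a randomized comparison, and nothing in 3.3.1, 3.6.1 or 3.8 brings them back for the 90-day assessment.

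The number affected cannot be estimated, because the documents give no reaction rate at this dose, and it is probably small. The ceiling of about 1 to 2 points in the NAC mean assumes that all subjects at the highest quoted event rate are lost and that they differ from the rest by 5 to 10 points. Neither is established. Loss of power is minor.

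The missing dosing steps for a mild suspected reaction or a pregnancy are worth writing down, but they are secondary.

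**What to change.** Amend 3.4.1 and 3.4.3 as follows.

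- A serious adverse event stops NAC but does not end study participation. Missed doses may stop NAC, at the PI's discretion, but likewise do not end participation.
- Doses held for safety do not count toward the 3.4.3 totals.
- All randomized subjects who have not withdrawn consent are invited to the already planned 90-day assessments that are safe for them (no SPECT if pregnant, consistent with 3.7.1), and are analysed in their assigned arm.

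As a secondary clarification, state that NAC is stopped for pregnancy, and held after a suspected hypersensitivity reaction until the PI has reviewed it.

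The cost is a few sentences of text and some real burden. Some subjects who would otherwise have left will attend the planned follow-up scan visit, with its radiation exposure. Some NAC subjects will be assessed off drug, which may slightly dilute the measured effect. No assessment is added to the schedule itself.
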